7.2 Security management in case of unexpected adverse effects

Each series of experiments will be supervised by a clinical doctor. Special attention will be paid to the possible occurrence of side effects, such as disinhibition, dizziness, nausea, drowsiness and respiratory impairment. In case of unexpected adverse effects, immediate help and quick transfer to an emergency unit is guaranteed.

8 Statistics

8.1 Primary and secondary endpoints

The primary endpoint of PUK-GHB01/02 is the detection of alterations in brain activity, GHB-, GABA-, and Glu-concentrations, and blood parameters after the administration of GHB. The secondary endpoint of trial I is the correlation between serum hormone levels and neurocognitive as well as subjective measures. The secondary endpoint of trial II is the correlation of blood parameters with cognitive alterations as well as subjective measures and the correlation of cerebral GHB-, GABA-, and Glu-concentrations with results of the other experiments GHB01 and GHB02.

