
3.2 Open questions

3.2.1 PUK-GHB01: social cognition and hormones

Since the discovery of GHB in the year 1960, an extensive body of research has been performed concerning its neurobiological effects in animals and humans. Its potency to induce pleasurable feelings, affiliative behavior and sexual arousal led to illicit use of GHB for recreational purposes. In spite of these facts, neither the prosocial and prosexual effects of GHB, nor the underlying neuroendocrine alterations were examined scientifically so far. Various hormones were shown to be involved in the processing of social cognition,

appetitive behavior and binding. It is most likely that the neuropeptide oxytocin plays a central role for the subjective and behavioral effects of GHB, as the secretion of this hormone was shown to correlate with the prosocial effects of the phenomenologically comparable club drug MDMA (Dumont et al., 2009). Other hormones of interest are centrally synthesized progesterone analogs such as alloprenanolon (3 α , 5 α -THP) and allotetrahydrodeoxy-corticosterone (THDOC). These neurosteroids are released after GHB application in rats and induce prosexual behavior (Barbaccia, 2004). Additionally, the results regarding the GHB-modulation of the HPA axis remain contradictory and need further investigation. The relations of GHB-mediated subjective and behavioral changes to alterations of cerebral activity and neuroendocrine function remain unstudied.

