3.3 Working hypotheses

We expect to find significant alterations of sexual arousal, social cognition, pharmacokinetics, depression and sleep biomarkers, cerebral GHB-, GABA-, and Glu-concentrations, resting state connectivity, cognition, and declarative memory functions after GHB administration compared to placebo. Moreover, we predict that these effects are correlated with specific changes in serum biomarker levels, brain activation patterns and sleep architecture, respectively.

4 Study design

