8.2 Number of subjects

Comparable studies to the effects of GHB and other challenges on neuroendocrine and cognitive parameters in awake and sleeping subjects (Carter et al., 2009a, Dumont et al., 2009, Grove-White and Kelman, 1971, Marshall et al., 2006) revealed effect sizes of $d=0.7-1.2$. With a conservative assumption of $d=0.7$, an α -error probability of 5%, and a power of 80% (two-tailed), we would need at least 19 subjects to detect significant differences in each experiment.

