8.4 Significance level

The significance level for both experiments will be $p \leq 0.05$ (=5%).

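### The secondary endpoints are open sets of correlations, with p ≤ 0.05 as the only significance rule and no lead pair, multiplicity control or exploratory label; if each is judged at that level, a false positive is likely.

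*Combined protocol and SAP*

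**What the plan says.** Section 8.1 gives each experiment a single secondary endpoint, worded as a correlation. For PUK-GHB01: "The secondary endpoint of trial I is the correlation between serum hormone levels and neurocognitive as well as subjective measures". For PUK-GHB02 there are two parts: blood parameters against cognitive and subjective measures, and "the correlation of cerebral GHB-, GABA-, and Glu-concentrations with results of the other experiments GHB01 and GHB02". The second part has no stated limit.

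Section 8.4 begins "The significance level for both experiments will be" and gives p ≤ 0.05. Section 8.3 names only repeated-measures ANOVA. Section 4.3.7 adds the software in which correlations will be analysed, but no method.

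Section 3.3 says of the expected drug effects: "Moreover, we predict that these effects are correlated with specific changes in serum biomarker levels, brain activation patterns and sleep architecture, respectively". Section 3.2.1 comes closest to naming a lead hormone: "It is most likely that the neuropeptide oxytocin plays a central role for the subjective and behavioral effects of GHB". Section 8 does not take this up, and no outcome measure is paired with oxytocin anywhere.

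**The concern.** The wording is singular, but each endpoint is a matrix of blood markers by tests and scales. With one 5% threshold and no statement of which correlation counts, the chance of some nominally significant result grows with the size of the matrix.

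The links between hormones and behaviour are part of the trial's rationale: section 3.1.1 gives them as an aim, and section 11.1 cites the understanding of such relationships in its risk-benefit argument. A chance correlation could therefore be reported as a finding. At these sample sizes it would also look substantial, because any correlation reaching p ≤ 0.05 has |r| of at least 0.35 (n = 32) or 0.44 (n = 20).

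**Working it through.** **The plan's own figure.** Section 8.2 concludes that "we would need at least 19 subjects to detect significant differences in each experiment", for d = 0.7, two-sided 5% and 80% power. A paired t-test with the noncentral t distribution gives n = 19 (power 82.3%), so the figure reproduces. It concerns a standardised difference; no correlation enters the sample size.

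**Counting the correlations, PUK-GHB01.** Section 4.2.1 lists:
- 8 conventional hormones: oxytocin, 3,5-THP, THDOC, ACTH, prolactin, testosterone, cortisol, progesterone;
- 9 further blood analytes, GHB among them (17 in all);
- 4 questionnaires, 4 social-cognition tests, 3 neuropsychology tests and 3 neuroeconomic tests.

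Section 8.1 does not say which tests are neurocognitive. With one score and one time point each:
- narrow reading (questionnaires plus neuropsychology): 8 × (4 + 3) = 56;
- wide reading (all instruments): 8 × (4 + 4 + 3 + 3) = 8 × 14 = 112;
- wide reading with all analytes: 17 × 14 = 238.

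Table 4 schedules 8 blood draws and 6 administrations of the GSQ, so subscales and repeats could raise these counts.

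**Counting, PUK-GHB02 (assumed).** Section 4.2.2 lists 21 blood markers other than genetic markers. I take 8 measures, which matches its 4 cognitive and 4 memory tests before any mood scale is added: 21 × 8 = 168. The brain-metabolite correlations are left out because the plan sets no limit on them.

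**Independent tests, no true correlation.** P(at least one p ≤ 0.05) = 1 − 0.95^m; expected false hits = 0.05 m.
- m = 56: 1 − 0.95^56 = 94.3%; 2.8 expected.
- m = 112: 1 − 0.95^112 = 99.7%; 5.6 expected.
- m = 168: 1 − 0.95^168 = 99.98%; 8.4 expected.

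**Allowing for dependence.** The documents give no correlations among hormones or among measures, so a range is needed. I simulated null data with the hormone block independent of the measure block, equal correlation ρ within each block, and Pearson tests at two-sided 5%. Chance of at least one false hit:

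| Set | ρ = 0 | ρ = 0.5 | ρ = 0.8 |
|---|---|---|---|
| 8 × 7, n = 32 | 94% | 78% | 41% |
| 8 × 14, n = 32 | over 99% | 91% | 52% |
| 21 × 8, n = 20 | 100% | 96% | 57% |

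At ρ = 0.9 the two PUK-GHB01 sets fall to 25% and 29%. The expected number of false hits does not depend on ρ.

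**Would choosing oxytocin alone suffice?** No. Against 14 measures, 1 − 0.95^14 = 51% if independent, and 35% at ρ = 0.5. A lead test needs both a hormone and a measure.

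**Effect of the remedy.** In the same kind of null simulation, Benjamini-Hochberg at 5% held the chance of any false hit to about 2–5%.

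**Power of a single lead correlation, n = 32.** By Fisher z, the |r| detectable with 80% power is tanh[(1.960 + 0.842)/√(32 − 3)] = tanh(0.520) = 0.48. A true r of 0.3 would have about 38% power.

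**The case against.** The strongest reply is that the plan never says how the correlations will be tested or what would count as meeting the endpoint. These are secondary endpoints of a mechanistic challenge study in healthy men, and a reader can judge r, n and p for himself. Much of this stands, and it rules out several stronger readings.

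- A reader might infer that each correlation is to be tested at 5%, and that one significant result meets the endpoint. The first is an inference from section 8.4, the only significance rule available; the second is written nowhere.
- A reader might infer that a false positive is nearly certain. That holds for weak to moderate dependence, but the chance is about one half at ρ = 0.8 and lower at 0.9.
- A reader might treat any particular test count as a minimum. Section 8.1 does not list the tests, so 56 is as defensible as 112. Going beyond the 8 conventional hormones also strains the endpoint's reference to hormone levels.
- A reader might take section 3.3 as a commitment to confirm the correlations, or conclude that any reported correlation is worthless. The section is headed as working hypotheses, and an estimate with its interval still informs.

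It is also fair to say that the primary outcomes in sections 4.1 and 8.1 are a long list under the same 5% level. Repairing the correlations does not address that.

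The reply does not remove the core point. A single 5% level over an open set, with no exploratory label, gives no protection against selecting the correlations that happen to pass.

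**Conclusion.** The concern holds in a conditional form. If each correlation is judged at the level in section 8.4, at least one false significant result is likely in each experiment when dependence is weak to moderate, and its chance stays far above 5% even when dependence is strong. Across ρ from 0 to 0.8 it runs from over 99% down to about 41% for PUK-GHB01, and from about 100% to 57% for the assumed PUK-GHB02 set.

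These figures rest on one score and one time point per instrument, no true associations, equal correlation within each block, and a PUK-GHB02 count that the plan does not supply. The repeats and subscales left out would add tests. Because the matter concerns secondary endpoints and is settled by wording, it should be corrected but does not threaten the trial's conduct.

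**What to change.** In section 8.1, label the correlations in both experiments exploratory. Report each with a confidence interval, and apply Benjamini-Hochberg control at 5% within each experiment's set. List the hormones, scores and time points that make up each set, so that its size is fixed.

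Optionally, the sponsor may name one lead hormone–measure pair for PUK-GHB01 before unblinding and test it at two-sided 5%. Section 3.2.1 supports oxytocin as the hormone; no measure is singled out, so that choice is the sponsor's. On days 1 and 2, sixteen men receive 20 mg/kg and sixteen 35 mg/kg (sections 2.2.1 and 4.7.2). A pooled n = 32 correlation could therefore reflect dose alone, and the lead analysis should adjust for or stratify by dose group.

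In section 8.4, state that the unadjusted 5% level does not apply to the exploratory correlations. Leave the level for the primary analyses in place, since no other is given.

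The cost is a few sentences and a routine step, with no new data or participants. Fewer correlations can be called significant, and a lead test at n = 32 has 80% power only for |r| of about 0.48.

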8.2 Number of subjects

Comparable studies to the effects of GHB and other challenges on neuroendocrine and cognitive parameters in awake and sleeping subjects (Carter et al., 2009a, Dumont et al., 2009, Grove-White and Kelman, 1971, Marshall et al., 2006) revealed effect sizes of $d=0.7-1.2$. With a conservative assumption of $d=0.7$, an α -error probability of 5%, and a power of 80% (two-tailed), we would need at least 19 subjects to detect significant differences in each experiment.

8.3 Statistical analyses

We will use repeated measurements ANOVA for all dependent variables in both experiments.

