4.3.6 Functional Magnetic Resonance Imaging (fMRI)

Functional Magnetic Resonance Imaging (fMRI) will be performed using the Philips Achieva 3.0 TX MR-System in the MR-Center of the University Hospital of Psychiatry Zurich. For functional imaging (fMRI), a T2*-weighted single-shot echoplanar sequence will be used in combination with an 8-channel head array (TE = 35 ms, TR = 3000 ms ($\theta = 82^\circ$), FOV = 220 mm, matrix = 80x80 reconstructed on 128 x128, voxel size: 2.75 x 2.75 x 4 mm, SENSE acceleration factor R = 2.0). Intrinsic functional connectivity at rest (Resting State [rs]-fMRI, 10 min), brain perfusion (Arterial Spin Labeling [ASL], 5 min) and brain anatomy (3D T1-weighted scan, 5 min) will be performed at baseline, followed by a post-Challenge Scan (rsfMRI/ASL: 12-15 min), an fMRI-Scan with the Sexual Arousal Task using the program Presentation® (Neurobehavioral Systems Neurobehavioral Systems, Inc. Albany, USA; 10-20 min) and a post-Task Scan (rsfMRI/ASL: 12-15 min). In the experimental nights 3+4 of PUK-GHB02, we will perform resting state fMRI/EEG scans.

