4.7 Bias reduction

4.7.1 Placebo

We will use a double-blind, randomized crossover design for bias reduction. The investigator, monitor, the data analysts and the study subjects will be kept unaware of the treatment assignment. A placebo will serve as comparator.

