6.1 Outcome measures GHB01

Experiment	Method	Time (related to GHB application)
PUK-GHB01		
days	Cambridge neuropsychological automated test	t -40 min

1+2	battery (CANTAB) 1	
	GHB specific questionnaire (GSQ)	t -17, +38, +66, +106, +138 min, t+ 180 min
	Profile of Mood States (POMS)	t -13, +63, +141, +183 min
	Sexual arousal and desire questionnaire (SADI)	t -10, +51, +103, +160 min
	Visual Analog Scale (VAS)	t - 15 min, + 40, + 68, + 108, + 140, + 182 min
	Sexual Arousal Task	t + 41 min
	Movie for the Assessment of Social Cognition (MASC)	t +109 min
	Multifaceted empathy test (MET)	t +74 min
	Social Value Orientation (SVO)	t +90 min
	Charity Donation (CD)	t +69 min
	Reciprocity Task (RT)	t +163 min
	Social gaze test (SGT)	t +143 min
	Blood tests for endocrinology (BS-endo)	t-30 min, t0, t + 20 min, t + 35 min, t + 65 min, t +95 min, t + 124 min and t + 180 min
CANTAB 2	t >24 h	
days 3+4	Baseline-Scan	t - 30 min
	Post-Challenge Scan	t + 40-55 min
	SAT Task-related Scan	t + 60-80 min
	Post-Task Scan	t + 85-100 min

Table 4 Outcome measures GHB01: methods and time of testing

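### Section 8.3 gives the same-session pre-dose values no role; if they count as time levels and the treatment main effect is tested, the GHB effect is diluted, and a baseline-adjusted post-dose contrast would be stronger for sustained effects

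*Combined protocol and SAP*

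**What the plan says.** Section 8.3 reads, in full: "We will use repeated measurements ANOVA for all dependent variables in both experiments". It names no factors, time levels, contrast or covariate, and nothing else in section 8 mentions a change score or a pre-dose reference. Section 8.2 assumes d = 0.7, two-sided 5% and 80% power, and concludes that "we would need at least 19 subjects to detect significant differences in each experiment". Section 4.7.1 sets the design: "We will use a double-blind, randomized crossover design for bias reduction".

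The schedules contain many same-session pre-dose values:

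- **GHB01 blood (6.1, Table 4):** the list begins "t-30 min, t0, t + 20 min" and has eight times, two of them at or before dosing.
- **GHB01 questionnaires (6.1):** GSQ, VAS, POMS and SADI each have one pre-dose value.
- **GHB01 imaging (4.3.6):** resting fMRI and perfusion "will be performed at baseline, followed by a post-Challenge Scan", with a further scan after the task.
- **GHB02 nights 1 and 2 (6.2):** blood and mood scales are taken before the 23:30 dose.
- **GHB02 nights 3 and 4 (6.2):** an MRI baseline at 23:00, then sessions from 00:05 and 08:30.

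Section 12.4 describes the efficacy part of the case report form as largely baseline values.

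**The concern.** Brain activity, GHB/GABA/Glu concentrations and blood parameters are the primary endpoints in 8.1, and many of them have a baseline in the same session. Two losses are possible when the analysis gives that baseline no defined place.

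First, if pre-dose times are ordinary levels of time, the treatment main effect averages over times at which the drug cannot have acted, so the estimate is pulled towards zero. Second, a main effect does not use the baseline to remove variation that is common to one session. A treatment-by-time test does remove it, but with several post-dose times it spreads a sustained effect over several degrees of freedom. Leaving the test unnamed also allows the choice between the two terms to be made after the data are seen. Estimates and type I error of a correctly specified ANOVA are not at issue; power on primary endpoints is.

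**Working it through.** **1. Reproduce the 19.** For a paired t-test, power = P(|T| > t(0.975, n−1)), where T is noncentral t with n−1 degrees of freedom and noncentrality 0.7√n. This gives 0.799 at n=18 and 0.823 at n=19, so 19 reproduces. An unpaired comparison would need 33 per arm, so d = 0.7 is a paired effect size. Power is 0.84 at n=20 and 0.97 at n=32.

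**2. Set-up.** Take the GHB-minus-placebo differences at k pre-dose and m post-dose times, with equal variance 1 and common correlation r. The documents do not give r, so it is assumed to range from 0 to 0.9. Assume a constant post-dose effect δ and fix d = 0.7 for the post-dose mean. Section 8.2 does not say which quantity d refers to, so that is also an assumption.

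- Variance of the post-dose mean: V = [1+(m−1)r]/m, so δ = 0.7√V.
- Main effect over all T = k+m levels: the mean effect is δ·m/T, with variance [1+(T−1)r]/T.
- Adjusted post-dose mean: variance V − r²/Vpre, with Vpre = [1+(k−1)r]/k (the covariate's degree of freedom is ignored here).

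Example, MRI/MRS (k=1, m=2) at r=0.5: V = 0.75 and δ = 0.606. The main effect has d = 0.606×0.667/√0.667 = 0.495. The adjusted contrast has d = 0.606/√0.50 = 0.857.

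**3. Main effect over all levels, at the planned n.**

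| Outcome | k/m | m/(k+m) | n | Power at r = 0 / 0.5 / 0.9 |
|---|---|---|---|---|
| GHB01 blood, pooled | 2/6 | 75% | 32 | 0.91 / 0.83 / 0.82 |
| GSQ, VAS | 1/5 | 83% | 32 | 0.94 / 0.90 / 0.89 |
| POMS, SADI | 1/3 | 75% | 32 | 0.91 / 0.84 / 0.82 |
| GHB01 resting fMRI/perfusion | 1/2 | 67% | 32 | 0.88 / 0.77 / 0.73 |
| GHB02 blood, nights 1-2 | 1/3 | 75% | 20 | 0.73 / 0.63 / 0.61 |
| GHB02 PANAS, VAMS, nights 1-2 | 1/4 | 80% | 20 | 0.76 / 0.68 / 0.66 |
| GHB02 MRI/MRS | 1/2 | 67% | 20 | 0.68 / 0.56 / 0.52 |

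For MRI/MRS the main effect would need n = 27 / 35 / 38 for 80% power. The blood row uses the eight times listed in 6.1, although 4.2.1 and 4.5.1 speak of six samples.

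**4. The alternatives, sustained effect, n=19, r = 0 / 0.5 / 0.9.** For MRI/MRS, treatment-by-time has 0.31 / 0.75 / about 1.00 and the adjusted post-dose mean 0.82 / 0.94 / about 1.00. For the GHB01 blood layout the figures are 0.15 / 0.83 / about 1.00 and 0.82 / 0.99 / about 1.00.

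**5. Simulation with explicit session effects** (assumed to be 30-70% of within-subject variance; effect 0.7 within-subject SD). This effect is smaller than a paired d of 0.7: it is 0.7/√2 = 0.49 at one scan. For the mean of two scans it lies between 0.7/√(2×0.7+0.3) = 0.54 and 0.7/√(2×0.3+0.7) = 0.61. The results therefore show the ordering of methods and should not be compared with the 80% in 8.2.

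- MRS, n=20, both scans respond: all-times main effect 36-48%; ANCOVA of the post-dose difference on the pre-dose difference 77-92%, with type I error about 5%.
- MRS, n=20, only the first scan responds: treatment-by-time 43-81%; adjusted post-dose mean 27-38%.
- Mixed model with subject as the only random effect: type I error 9-14% (MRS, n=20) and 17-24% (hormones, n=16). Values from one session share a session effect that such a model treats as independent noise.

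**6. Worst case for adjustment.** With no session effect (MRS, n=20, d = 0.7 on the post-dose mean), power is 82% adjusted against 84% for the unadjusted post-dose mean, 68% for the main effect and 32% for treatment-by-time.

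**The case against.** The strongest reply is that the dilution is inferred. Several stronger readings are tempting, and the documents do not support them.

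- **That the plan counts pre-dose values as outcome levels.** Section 8.3 does not say so. This is one reading of an unspecified model, which is why the dilution is stated conditionally.
- **That neither ANOVA term uses the baseline.** The treatment-by-time term does: a stable session effect cancels in it. With one value before and one after dosing, as in the word-list recall of 4.3.4, it is the change-score test.
- **That the sample size is wrong, or that 80% power is lost throughout.** The 19 is correct for a paired contrast. Pooled GHB01 blood at n=32 keeps 82-91% even when diluted. The n=16 figures concern single dose groups only.
- **That every outcome has a baseline.** SAT, MET, polysomnography and the blood on nights 3-4 have none in the session, and on experimental nights the Karolinska test and morning questionnaire come only after dosing. In 6.2 the pre-dose MRS entry names no region and fits within 30 minutes, whereas the post-dose session names three regions over 95 minutes. A baseline for each voxel is not established.
- **That the adjusted post-dose mean is always better.** For a short-lived effect the ordering reverses (step 5).

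These points limit the concern but do not remove it. Section 8 leaves collected baselines unused, and a stronger contrast is available from the same data where the effect is sustained.

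**Conclusion.** The point holds as a conditional one and should be acted on. Section 8.3 gives the scheduled pre-dose values no role. If they are time levels and the main effect is tested, the effect falls to 67-83% of its post-dose size for the outcomes tabulated. GHB02 MRI/MRS is hit hardest, with about 52-68% power at n=20 when the post-dose mean has a paired d of 0.7. GHB01 resting fMRI has about 73-88% at n=32, and pooled GHB01 blood stays at or above 80%. For a sustained effect, the baseline-adjusted post-dose contrast does better than the main effect and at least as well as treatment-by-time.

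These figures rest on equal correlation between times, an assumed r, a constant post-dose effect, and d = 0.7 referring to the post-dose mean. The gain from adjustment is nil at r = 0 and grows with r.

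**What to change.** Add a paragraph to 8.3 covering outcomes with a pre-dose value in the same session:

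1. Take pre-dose times out of the outcome levels. Adjust for the same-session pre-dose value: the mean of t−30 and t0 for GHB01 blood, the baseline scan for fMRI, and for MRS only where the same voxel was measured at baseline. Enter it within subject, for example as the deviation from the subject's mean baseline.
2. Fit a crossover model with treatment, post-dose time, treatment-by-time, period and sequence, and random effects for **both** subject and subject-by-session. For the post-dose mean, an ANCOVA of the GHB-minus-placebo post-dose difference on the pre-dose difference serves the same purpose. The session term must not be dropped, given the type I error shown in step 5.
3. Name in advance, per outcome, whether the test is the post-dose mean or the baseline-adjusted time-specific effect. Use the latter where a short-lived effect is expected.
4. State that outcomes without a same-session pre-dose value are analysed without the covariate.

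The cost is one paragraph, one degree of freedom per model, and about two points of power if sessions share no common variation. No new data are needed where the baseline already exists; for MRS, the plan should confirm which voxels the pre-dose scan covers.
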